6.5.3.2 Statistical Methods

The presentation of vital signs focuses on the descriptive summaries at baseline, at 10 minutes, and at 1 hour post-OPTISON administration, and the change from baseline to the 10-minute and 1-hour post-OPTISON assessments. All subjects in the safety population who have a baseline and a post-baseline assessment of vital signs will be included in the presentation of the results. Results will be presented by weight group (≤ 40 , > 40 kg) and overall.

In addition to the change from baseline results, the shifts from baseline to the post baseline visit will be summarized in tabular form for heart rate and systolic blood pressure. Subjects will be classified at baseline and the post-baseline visit in one of the following categories based on a comparison of the vital sign result to the reference range

for that vital sign parameter: below normal, normal, or above normal. A shift table will be constructed in which each subject is cross-classified based upon the reference range categories. The number and percentage of subjects in each shift table cell will be displayed. The number of subjects in the safety population missing either baseline or post-baseline vital sign information will also be presented. Results will be presented by weight group and overall. All vital signs results will be listed. Classification (below normal, normal, or above normal) will be presented in the listing for respiratory rate, heart rate, systolic blood pressure, and pulse oximetry.

6.5.4 Analysis of ECG Parameters

6.5.4.1 Variables and Criteria Defining Abnormality

A 12-lead ECG will be measured at the various pre- and post-treatment time point ranges described in [Table 2](#). The ECGs will be characterized as normal or abnormal, and, if abnormal, whether the abnormality is clinically significant. These overall readings will be an interpretation based on ECG intervals (heart rate, PR, RR, QRS, QT, QTcF [Fridericia]). QTcF will be defined as follows:

- Fridericia's correction (QTcF): $QT_C F = QT / \sqrt[3]{RR}$
- Bazett's correction (QTcB): $QT_C B = QT / \sqrt{RR}$

Normal ranges for the observed values and change from baseline by age group are defined in [Table 5](#), [Table 6](#) and Table 7.

Table 5 Mean and Percentiles of ECG Cardiac Measures Among Pre-pubertal Children

ECG Variable	Mean (sd)	1 st %ile	5 th %ile	Median	95 th %ile	99 th %ile
Heart Rate (bpm)	83.0 (12.1)	59	65	82	104	114
RR Interval (ms)	738.5 (107.8)	526.3	576.9	731.7	923.1	1040
PR Interval (ms)	132.8 (17.3)	100	108	130	162	180
QRS Interval (ms)	80.0 (9.0)	64	70	80	96	102
QT Interval (ms)	354.7 (24.3)	300	318	352	396	416
QTc Bazett (ms)	414.0 (19.6)	367	383	414	443	460
QTc Data-derived (ms)	399 (17.3)	357.4	372	398.7	424.1	439.6
QTc Fridericia (ms)	393.2 (17.1)	353.3	366.3	392.9	419	433

Note: Pre-pubertal group (N = 1537) defined as females whose age was \leq 8 years (n = 224) and males whose age was \leq 9 years (n = 1313). Source: Child and Adolescent Psychiatry and Mental Health 2007;1:11

Table 6 Mean and Percentiles of ECG Cardiac Measures Among Pubertal Children

ECG Variable	Mean (sd)	1 st %ile	5 th %ile	Median	95 th %ile	99 th %ile
Heart Rate (bpm)	77.4 (11.8)	54	60	76	98	109
RR Interval (ms)	792.9 (121.1)	555.6	612.2	780	1000	1132
PR Interval (ms)	136.8 (18.5)	100	112	136	170	190
QRS Interval (ms)	83.0 (9.1)	68	70	80	96	106
QT Interval (ms)	368.8 (27.0.)	310	330	368	412	440
QTc Bazett (ms)	415.6 (21.3)	362	381	416	448	468
QTc Data-derived (ms)	403.9 (19.1)	357	373.3	404	433.1	450.1
QTc Fridericia (ms)	399.4 (19.0)	354.5	369.4	399.6	429	443.9

Note: Pubertal group (N = 3656) defined as females whose age was > 8 and \leq 13 years (n = 881) and males whose age was > 9 and \leq 14 years (n = 2775). Source: Child and Adolescent Psychiatry and Mental Health 2007;1:11

Table 7 Mean and Percentiles of ECG Cardiac Measures Among Post-pubertal Children

ECG Variable	Mean (sd)	1 st %ile	5 th %ile	Median	95 th %ile	99 th %ile
Heart Rate (bpm)	70.8 (11.4)	48	52	70	91	102
RR Interval (ms)	870.3 (144.3)	588.2	659.3	857.1	1153.8	1250
PR Interval (ms)	140.8 (18.9)	104	116	140	176	192
QRS Interval (ms)	87.8 (9.9)	70	72	88	104	112
QT Interval (ms)	382.9 (29.0)	328	340	380	432	470
QTc Bazett (ms)	412.2 (20.7)	350	376	413	444	457
QTc Data-derived (ms)	405.0 (18.5)	357.2	371.6	406.5	433	447.5
QTc Fridericia (ms)	402.1 (18.5)	354.5	371.1	402.6	430.9	446.5

Note: Post-Pubertal group (N = 737) defined as females whose age was >13 yrs (n = 240) and males whose age was > 14 yrs (n = 497). Source: Child and Adolescent Psychiatry and Mental Health 2007;1:11

6.5.4.2 Statistical Models

All subjects in the safety population who have a baseline and a post-baseline assessment of ECG data will be included in the presentation of the results. Overall ECG investigator interpretation will be categorized as normal, abnormal (Not Clinically Significant), and abnormal (Clinically Significant). Number and percentage of subjects in each category at each timepoint will be presented.

Consistent with ICH E14 guidance, ECG data will be presented both as analyses of central tendency (e.g., means, medians) and categorical analyses. ECG data will be summarized overall and by weight group (\leq 40, $>$ 40 kg).

Twelve-lead ECG data (observed values and changes from baseline) will be presented using descriptive statistics by weight group (≤ 40 , > 40 kg) and overall for each time point (baseline, 10 minutes, and 30 minutes post-dose).

In addition to the observed values and change from baseline results, the shifts from baseline to post-baseline time points will be summarized in tabular form for each ECG parameter and the overall interpretation. The overall interpretation will be based on the categories of the interpretation listed previously, while the ECG parameters will be listed based on being below normal ($< 1^{\text{st}}$ percentile), normal, or above normal ($> 99^{\text{th}}$ percentile) compared to the reference ranges in [Table 5](#), [Table 6](#) and Table 7. The number and percentage of subjects in each shift table cell will be displayed. The number of subjects who are missing either baseline or post-baseline ECG data will also be provided for each timepoint.

All ECG results will be listed including overall interpretation and status compared to normal ranges (below normal / normal / above normal).

In addition, changes from baseline in the QTc interval will be displayed according to the Committee for Medicinal Products for Human Use (CHMP) criteria (absolute QTc interval prolongation, of > 450 , > 480 , > 500 ms and change from baseline in QTc interval > 30 and > 60 ms).

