12.7 Procedures for Missing, Unused and Spurious Data

Missing values will not be substituted by estimated values, but treated as missing in the statistical evaluation. All data from all subjects dosed in the study will be included in all listings, plots, summary tables, and statistical analyses when appropriate.

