12.8 Rules for Excluding Subjects from Analysis

All dosed subjects will be included in the analyses unless otherwise specified. The sponsor will make any decisions regarding whether any subjects or any individual values belonging to a subject will be excluded from the evaluations when the protocol violation is considered to have a negative impact on the scientific aspects and interpretation of the study results. If the subject has received any IMP, all available safety data will be used. The reason(s) for any exclusion will be described in the report.

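### The SAP's ECG rule requiring both a baseline and a post-baseline value is not confined to change and shift outputs, so as written it also restricts summary tables that need no baseline, including absolute QTc categories

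*SAP*

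**What the plan says.** SAP 6.5.4.2 begins its ECG methods with a rule on who is shown: "All subjects in the safety population who have a baseline and a post-baseline assessment of ECG data will be included in the presentation". It then plans these outputs:

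- the investigator's overall interpretation: "Number and percentage of subjects in each category at each timepoint will be presented";
- observed values and changes at baseline, 10 minutes and 30 minutes;
- shift tables, with a missing-data count: "The number of subjects who are missing either baseline or post-baseline ECG data will also be provided for each timepoint";
- a listing: "All ECG results will be listed including overall interpretation and status compared to normal ranges";
- a QTc display, in which "changes from baseline in the QTc interval will be displayed according to the Committee for Medicinal Products for Human Use" criteria. It combines absolute categories (above 450, 480 and 500 ms) with change categories (above 30 and 60 ms).

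No output has a denominator of its own. The list of outputs in SAP Section 8 labels the interpretation table (14.3.4.3) and the QTc outlier table (14.3.4.5) simply as Safety. SAP 4.1.1 defines that population by at least one administration of OPTISON.

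For vital signs, SAP 6.5.3.2 says: "All subjects in the safety population who have a baseline and a post-baseline assessment of vital signs will be included in the presentation". Protocol 12.4.1 has the same sentence.

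On the use of safety data, Protocol 12.8 says: "If the subject has received any IMP, all available safety data will be used". Protocol 12.7 says: "All data from all subjects dosed in the study will be included in all listings, plots, summary tables, and statistical analyses when appropriate".

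**The concern.** A change from baseline or a shift cannot be computed without a baseline, so a both-values condition is natural there. An observed QTc at 10 minutes, an interpretation at 30 minutes or a QTc above 500 ms needs only the post-dose recording. Applying the condition to these outputs is a complete-case restriction with no statistical need behind it.

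What is at stake is an ECG abnormality seen after dosing in a child with no usable baseline. It would be missing from the safety table meant to show it, and the denominator would differ from the one used for adverse events. Safety is a secondary objective, Protocol 10.3.5 states that the paediatric adverse event profile is not yet established, and the sample has been reduced to 30 evaluable subjects. One child can therefore decide whether a row reads zero.

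**Working it through.** The plan gives no figure for this point. The check is a comparison of texts, followed by an illustration of size.

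**Which outputs need a baseline**

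| Output in SAP 6.5.4.2 | Baseline needed? | Within the both-values rule as written? |
|---|---|---|
| Change from baseline, shift tables, QTc change >30 and >60 ms | Yes | Yes |
| Observed values at 10 and 30 minutes | No | Yes |
| Overall interpretation by time point (14.3.4.3) | No | Yes |
| Absolute QTc >450, >480, >500 ms (part of 14.3.4.5) | No | Yes |
| Listing of all ECG results | No | No; all are listed |

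**Where each rule comes from**

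- ECG: Protocol 12.4.2 plans observed values, changes, shifts and QTc categories with no both-values condition. The SAP adds one, and the table of changes in SAP Section 9 does not mention it.
- Vital signs: the condition is already in Protocol 12.4.1, so the SAP changed nothing. SAP 6.5.3.2 plans observed values, changes and shifts but no absolute-threshold table, so only the observed-value summaries are affected.
- Physical examination: SAP 6.5.5 uses the safety population and counts missing data, with no both-values condition.
- Precedence: SAP Section 1 lets the SAP prevail over the protocol on planned analyses, so Protocol 12.8 does not settle the matter for a programmer.

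**Size, for illustration.** Assume 30 children, borrowing the 30 evaluable subjects in SAP 2.3; the Safety population may differ. Limits are exact (Clopper-Pearson) 95%. With no events the upper limit is 1 − 0.025^(1/n).

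- One child has a post-dose QTc above 500 ms and no baseline, and the rule is applied: 0/29 = 0%, upper limit 1 − 0.025^(1/29) = 11.9%.
- Same child, counted: 1/30 = 3.3%, limits 0.1 to 17.2%.
- No events and 0, 1, 2 or 3 children without a baseline: upper limits 11.6%, 11.9%, 12.3% and 12.8%. Precision barely moves.
- With 50 children: 0/49 (upper limit 7.25%) against 1/50 = 2.0% (0.05 to 10.65%).

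**How likely.** The documents give no rate p of unusable baseline ECGs. Assuming p of 1 to 5% per child, independently, the chance that at least one of 30 is lost is 1 − (1 − p)^30: 1 − 0.99^30 = 26% to 1 − 0.95^30 = 79%. That is the chance of losing a child, not of changing a finding. If exactly one child has the notable value and missingness is unrelated to it, the chance that this child lacks a baseline is p itself, 1 to 5%.

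**The case against.** The case for leaving the text alone has several parts.

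- *The data are not lost.* All ECG and vital-sign results are listed, and subjects missing either value are counted. This stands. A reader might infer that a child without a baseline disappears from every result; the documents do not support that. But a listing does not correct the numerator or denominator of a summary table.
- *The rule says who is included, not that others are excluded.* The word only is absent, and the Safety labels point to a wider denominator. This stands in part: exclusion is the plain reading but not a certainty. Still, an inclusion condition naming both values has no function unless children lacking one are left out.
- *The protocol's general rules are qualified.* Protocol 12.7 is limited to what is appropriate. Protocol 12.8 allows for other specification, and its safety-data sentence follows text on exclusions for protocol violations. Neither promises that every value enters every table. This stands, so the ECG rule is better called a poor fit with Protocol 12.8 than a flat contradiction.
- *The vital-sign rule is the protocol's own.* This stands. A reader might see an unrecorded SAP change there too, but only the ECG rule is new.
- *The restriction need not favour the product.* A reader might infer that it can only hide abnormalities. It also removes normal values: with one event in a child who is kept, dropping a normal child gives 1/29 = 3.4% instead of 1/30 = 3.3%.
- *It should rarely apply.* Protocol 9.2 requires the baseline ECG and vital signs before dosing, and SAP Section 5 takes the last non-missing pre-dose value, which unscheduled recordings can supply. This stands and keeps the point small.

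**Conclusion.** The point holds as a minor but specific clarification. As written, SAP 6.5.4.2 applies a both-values condition to three kinds of ECG summary that need no baseline. That condition is new in the SAP and unrecorded in Section 9, and it leaves the denominators of Tables 14.3.4.3 and 14.3.4.5 open to two readings. For vital signs the same wording matters only for observed-value summaries and is inherited from the protocol.

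The expected effect is small, possibly nil. The worst case is one notable post-dose value shown as 0/29 instead of 1/30. It requires the child with that value to be the one lacking a baseline, and it rests on the assumed 30 children. The 26 to 79% range should not be read as a measure of impact: its 1 to 5% input is an assumption, and it counts lost children rather than altered findings.

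**What to change.** In SAP 6.5.4.2 and 6.5.3.2, apply the both-values condition only to change-from-baseline and shift outputs, including the QTc change categories above 30 and 60 ms. For observed values, overall ECG interpretation by time point and absolute QTc categories, use every Safety-population child with a value at that time point, and state this denominator in Tables 14.3.4.3 and 14.3.4.5. Because the vital-sign wording comes from Protocol 12.4.1, record that change in SAP Section 9.

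The cost is about two SAP sentences and no new data. The one downside is that n will differ slightly between observed-value and change columns; SAP Section 5 already includes n in the summary statistics for continuous variables.

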6.5.5 Analysis of Physical Examination

Physical examination findings at baseline and after OPTISON administration will be summarized for the safety population in the form of a shift table. Findings for each body system will be categorized as normal, abnormal (non-clinically significant), and abnormal (clinically significant). The number and percentage of subjects in each shift table cell will be displayed. The number of subjects who are missing either baseline or post-baseline Physical examination data will also be provided for each timepoint. Data will be presented by weight group (≤ 40 , > 40 kg) and overall.

8 LIST OF TABLES, FIGURES AND DATA LISTINGS THAT ARE TO BE PROGRAMMED

Whenever applicable, tables listed below will present results overall and by weight group and will be repeated by reader.

TABLE NUMBER	TABLE TITLE	POPULATION FOR ANALYSIS
14.1.1	Summary of Subject Disposition	All Subjects
14.1.2.x	Summary of Subject Demographics	Safety, FAS, PP
14.1.3	Summary of Medical History	Safety
14.1.4.1	Summary of Prior Medications	Safety
14.1.4.2	Summary of Concomitant Medications	Safety
14.1.5	Summary of Exposure to OPTISON	Safety
14.2.1.1a	Summary of Visualization of LV Wall by Segments	ITT
14.2.1.1b	Summary of Visualization of LV Wall by Segments	PP
14.2.1.2a	Summary of Visualization of LV Wall Overall	ITT
14.2.1.2b	Summary of Visualization of LV Wall Overall	PP
14.2.2a	Summary of Peak Contrast Intensity in LV	ITT
14.2.2b	Summary of Peak Contrast Intensity in LV	PP
14.2.3a	Summary of Peak Contrast Filling in LV	ITT
14.2.3b	Summary of Peak Contrast Filling in LV	PP
14.2.4a	Summary of Contrast Enhancement Duration in LV	ITT
14.2.4b	Summary of Contrast Enhancement Duration in LV	PP
14.2.5a	Summary of Image Quality	ITT
14.2.5b	Summary of Image Quality	PP

TABLE NUMBER	TABLE TITLE	POPULATION FOR ANALYSIS
14.2.6a	Summary of Diagnostic Usefulness	ITT
14.2.6b	Summary of Diagnostic Usefulness	PP
14.2.7a	Summary of Diagnostic Confidence of LV EBD and Wall Motion Between Contrast and Non-Contrast Enhanced Images	ITT
14.2.7b	Summary of Diagnostic Confidence of LV EBD and Wall Motion Between Contrast and Non-Contrast Enhanced Images	PP
14.2.8a	Summary of Diagnostic Confidence of LVEF Between Contrast and Non-Contrast Enhanced Images	ITT
14.2.8b	Summary of Diagnostic Confidence of LVEF Between Contrast and Non-Contrast Enhanced Images	PP
14.2.9a	Summary of LV Function Assessed by LVEF	ITT
14.2.9b	Summary of LV Function Assessed by LVEF	PP
14.2.10a	Summary of Dose Suitability	ITT
14.2.10b	Summary of Dose Suitability	PP
14.3.1	Overall summary of Treatment Emergent Adverse Events	Safety
14.3.1.1	Summary of Treatment Emergent Adverse Events by System Organ Class and Preferred Term	Safety
14.3.1.2	Summary of Treatment Emergent Adverse Events by maximum severity by System Organ Class and Preferred Term	Safety
14.3.1.3	Summary of Treatment Emergent Adverse Events considered related to IMP by System Organ Class, Preferred Term	Safety
14.3.2.1	Summary of Serious Treatment Emergent Adverse Events by System Organ Class and Preferred Term	Safety
14.3.2.4	Summary of Treatment Emergent Adverse Events Leading to Study drug Discontinuation by System Organ Class and Preferred Term	Safety
14.3.3.1	Summary and Change from Baseline – Vital Signs	Safety
14.3.3.2	Shifts from Baseline to Post-Administration Timepoints – Vital Signs	Safety
14.3.4.1	Summary and Change from Baseline – Electrocardiograms	Safety
14.3.4.2	Shifts from Baseline to Post-Administration Timepoints – Electrocardiograms	Safety
14.3.4.3	Summary of Overall Interpretation by Timepoint - Electrocardiograms	Safety
14.3.4.4	Shift from Baseline to Post-Administration Timepoints of Overall Interpretation - Electrocardiograms	Safety
14.3.4.5	Summary of QTc Interval Outlier Categories	Safety
14.3.5	Shift from Baseline to Post-Administration Timepoint – Physical Examination	Safety

LISTING NUMBER	LISTING TITLE	POPULATION FOR ANALYSIS
16.2.1	Subject Disposition	All Subjects
16.2.2	Protocol Deviations	All Subjects
16.2.3	Inclusion/Exclusion Criterion	All Subjects
16.2.4.1	Demographic Information	Safety
16.2.4.2	Medical History	Safety
16.2.4.3	Prior and Concomitant Medications	Safety
16.2.5	Exposure to OPTISON	Safety
16.2.6.1	Visualization of Segments	ITT
16.2.6.2	BIE Interpretations	ITT
16.2.6.3	Non-Contrast and Contrast Enhanced Comparisons	ITT
16.2.6.4	Dose Suitability	ITT
16.2.7.1	Adverse Events	Safety
16.2.7.2	Deaths	Safety
16.2.7.3	Serious Adverse Events	Safety
16.2.7.4	TEAEs leading to discontinuation of study treatment	Safety
16.2.8.1	Vital Signs	Safety
16.2.8.2	Electrocardiogram – Reader Results	Safety
16.2.8.3	Electrocardiogram – Overall Interpretation	Safety
16.2.8.4	Physical Examination	Safety

9 SUMMARY OF CHANGES

Changes from the statistical analyses planned in the protocol are summarized in the following table:

Protocol Amendment A01 Version 2.0	Changes
ITT population All subjects enrolled in the study who have available non-contrast harmonic images and OPTISON-enhanced echocardiographic images, irrespective of the quality of CE-ECHO.	For consistency with ICH E9 guidance, the efficacy population has been renamed from ITT population to Full Analysis Set. The PP Population definition has been updated to all subjects in the FAS population who do not have important protocol deviation impacting the study primary endpoint. A lack of contrast enhancement is not considered as a protocol deviation. Nevertheless, any important deviation from the Imaging Manual (e.g. wrong settings for echocardiographic imaging, standard apical 4-chamber and 2-chamber views not acquired...) will be reviewed during the Data Review Meeting and exclusion from the PP Population will be assessed.
All summary tables and data listings will be separated by dose levels.	Whenever relevant, summaries and listings will be presented by Weight group (≤ 40 , > 40 kg) and dose level.
Medications will be presented by ATC Class 1 and preferred term	Prior and concomitant medications will be tabulated by ATC Class 3 and preferred term
Primary endpoint analysis	Supportive analyses added in Section 6.4.2

Reference ranges for Vital signs	Adolescent (13+ yrs.) category added in Reference ranges table Table with reference ranges for Post Pubertal Children added
Reference ranges for ECG	Table with reference ranges for Post Pubertal Children added

Any deviations from the statistical analysis outlined in the SAP will be described, and reasons for the deviations listed, in the final Clinical Study Report.

10 APPENDIX

Not applicable
